10.0 STUDY COMMITTEES

10.1 Executive Operations Committee (EOC)

The EOC is comprised of the Coordinating Investigator(s) and selected members of the Medtronic Clinical Research Department. Additional individuals may be consulted as appropriate (e.g. Angiographic Core Laboratory personnel, etc.).

The EOC will be responsible for assisting Medtronic with the oversight of the clinical study. This committee will meet periodically by teleconference to discuss subject enrollment and clinical site progress, as well as generally assist sites with the successful conduct of the study. The EOC will be responsible for reviewing the final results, determining the methods of presentation and publication, and selection of secondary projects and publications.

10.2 Data Monitoring Committee (DMC)

The DMC is composed of at least five members with pertinent expertise (clinicians and at least 1 biostatistician) who are not participants or directly involved in the conduct of the study.

The responsibility of the DMC is to evaluate safety data on an ongoing basis and to advise Medtronic about the continuing safety of the study, in order to ensure the well-being of the current participants and those yet to be enrolled as well as the continuing validity and scientific merit of the study.

Additionally, cumulative reports will be reviewed by the DMC during the follow-up period. Based on the safety data, the DMC may recommend that Medtronic modify or stop the study. All final decisions regarding study modifications or termination will be made by the Medtronic.

10.3 Clinical Events Committee (CEC)

The CEC is comprised of clinicians (interventional and non-interventional) with pertinent expertise who are not participants in the study and who do not have any other real or potential conflicts of interest. The CEC is charged with the development of specific criteria used for the categorization of adverse events and clinical endpoints in the study. Criteria will be established for selected complications and clinical events.

At the onset of the study, the CEC will establish explicit rules outlining the minimum amount of data required and the algorithm followed in order to classify an event.

The Medtronic Clinical Operations Safety Department (MCO Safety) will categorize all clinical events. They will provide this information to the CEC. The CEC will meet regularly to review and adjudicate all events in which the required minimum data are available.

RESOLUTE Onyx 2.0 mm Clinical Study
CONFIDENTIAL - May not be reproduced without written permission from Medtronic

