1.3 Design

Single arm, open label multicenter trial

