7.4 Analysis of the Primary Endpoint

The number and percentage of subjects with 12-month TLF will be provided. A one-sided upper 95% confidence interval of the Resolute Onyx 2.0 mm stent 12-month TLF rate will be calculated through binomial (exact) method. If this upper limit is below 19%, the clinical objective will be considered to have been met.

With regard to clinical outcomes analysis, in subjects receiving treatment of two lesions with a Resolute Onyx 2.0 mm stent, the lesion to be included in the primary analysis, the “analysis lesion”, will be randomly selected at the time of analysis. For subjects receiving treatment of a Resolute Onyx 2.0 mm stent and another size stent, the primary analysis will include the lesion treated with the 2.0 mm stent, regardless of the other stent size. A secondary analysis will be conducted for all target lesions.

Statistical non-significance in the primary endpoint for gender comparisons will confirm the homogeneity by gender in this trial.

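### Protocol 10.3 passes the sponsor's event category to the Clinical Events Committee, and nothing as written withholds it until the committee has decided

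*Protocol*

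**What the plan says.** Protocol 10.3 sets out the steps in this order:

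1. The sponsor's safety department acts on every event and hands over the result: "The Medtronic Clinical Operations Safety Department (MCO Safety) will categorize all clinical events. They will provide this information to the CEC".
2. The committee then decides: "The CEC will meet regularly to review and adjudicate all events in which the required minimum data are available".

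The same section gives the CEC real authority. Its members are clinicians who take no part in the study and have no conflicts of interest. It writes the classification criteria ("The CEC is charged with the development of specific criteria used for the categorization of adverse events and clinical endpoints in the study") and fixes its procedure in advance ("At the onset of the study, the CEC will establish explicit rules outlining the minimum amount of data required and the algorithm followed").

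Protocol 1.3 describes the design as "Single arm, open label multicenter trial". Protocol 7.4 and SAP 6.2 compare one observed TLF rate with a fixed goal, using the exact one-sided 95% upper limit: "If this upper limit is below 19%, the clinical objective will be considered to have been met".

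**The concern.** A committee that has the sponsor's classification when it opens a case may start from that classification. This matters only where the definitions leave room for judgement. In Protocol Appendix 2 that room exists in four places:

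- **Death:** whether a non-cardiac cause is unequivocal.
- **Target-vessel MI:** whether the infarct territory clearly belongs to another vessel.
- **Clinically-driven TLR:** with stenosis from 50% to below 70%, whether there were ischemic symptoms or a positive functional study.
- **MI with missing biomarkers:** left to the CEC on the clinical scenario.

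In a randomized trial with masked adjudication, a pull of this kind would tend to act on both arms. Here there is one arm, and any shift goes directly into the rate compared with 19%. The pass mark is a small count, so very few events can decide the result.

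**Working it through.** **Inputs.** Performance goal 19% (Protocol 7.1); assumed true TLF rate 9.4%, one-sided level 0.05, 100 subjects and 10% loss, hence 90 evaluable (Protocol 7.2, SAP 3.3); exact binomial upper limit (Protocol 7.4, SAP 6.2).

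**The plan's own figure.** Protocol 7.2 claims more than 80% power. The normal approximation, Φ{[(p0 − p1)√n − 1.645√(p0(1 − p0))] / √(p1(1 − p1))} with p0 = 0.19, p1 = 0.094 and n = 90, gives 81.8% and so reproduces the claim. The planned exact rule gives 77.6% at n = 90 and 85.5% at n = 100. That difference is a separate matter, but it confirms that the inputs are read correctly.

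**Pass mark.** The exact upper limit for x events in n is the 95th percentile of Beta(x + 1, n − x).

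| n | Events | Upper limit | Result |
|---|---|---|---|
| 90 | 10 | 18.1% | pass |
| 90 | 11 | 19.4% | fail |
| 100 | 12 | 18.7% | pass |
| 100 | 13 | 19.9% | fail |

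**How often one event moved out of TLF changes the result.** Only a trial that stands one event above the pass mark is affected. At a true rate of 9.4%:

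- n = 90: P(X = 11) = 8.6%
- n = 100: P(X = 13) = 5.9%

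**False-pass chance at a true rate of 19%.** This is a hypothetical in which one true TLF event is moved out in every trial, so that the effective pass mark rises by one:

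- n = 90: P(X ≤ 10) = 3.2% becomes P(X ≤ 11) = 6.1%
- n = 100: P(X ≤ 12) = 4.3% becomes P(X ≤ 13) = 7.6%

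**Range under an assumed miss rate.** The documents give no misclassification rate. If each true TLF event were independently missed with probability m, the false-pass chance would be P(X ≤ pass mark) at a rate of 0.19(1 − m):

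| m (assumed) | n = 90 | n = 100 |
|---|---|---|
| 0 | 3.2% | 4.3% |
| 5% | 5.2% | 6.9% |
| 10% | 8.0% | 10.8% |
| 20% | 17.6% | 23.0% |

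These figures show how sensitive the result is to small counts. They do not measure anchoring.

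**The case against.** **The text does not state that voting members see a sponsor verdict on TLF.** A reader might infer that the endpoint is adjudicated with the sponsor's answer in view. That rests on the order of the sentences in 10.3. Categorizing could mean sorting by event type, and Protocol 8.3.2 does give the same department a separate sorting task, the check of every SAE against the UADE definition. The CEC's detailed rules are not in the documents, so its actual practice cannot be seen. This stands as a limit on the claim. But 10.3 itself applies the word categorization to clinical endpoints as well as adverse events, and neither document says that the category is withheld.

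**The safeguards are substantial.** The CEC is independent, writes its own criteria and sets its algorithm at the start. Appendix 2 resolves doubt against the device: deaths that are unwitnessed or of unknown cause count as cardiac, and an MI counts as target-vessel unless clearly due to another vessel. TLR has numeric QCA limits, and MI rests mainly on enzyme multiples in a fixed order. This stands too, and it narrows the set of contestable events. It does not empty it, and one event can suffice.

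**The size is easily overstated.** A reader might add P(10) = 11.5% and P(11) = 8.6% at n = 90 and conclude that one classification decides about 20% of trials. For a shift out of TLF that is wrong, because a trial with 10 events already passes. Nor may the 6.1% or 7.6% be read as the trial's actual type I error: each assumes a certain reclassification in every trial, and no document supports such a rate.

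**Conclusion.** The point holds as an avoidable exposure. Protocol 10.3, read plainly, sends the sponsor's category to the CEC before adjudication, and nothing as written keeps it from the committee when it decides components that retain some judgement. The documents do not show that bias occurs, how large it would be, or in which direction it would run.

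At the assumed 9.4%, the share of trials in which one event moved out of TLF would turn a fail into a pass is 8.6% with 90 evaluable subjects and 5.9% with 100. These figures assume independent binomial outcomes and the exact decision rule. The false-pass figures are conditional on the misclassification assumed for each of them.

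The exposure is modest, but the change that removes it is simple enough to be worth making.

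**What to change.** Amend Protocol 10.3 so that MCO Safety assembles and forwards the source documents for each event, and its own category is withheld until the CEC has recorded its verdict. The sponsor may still use its category for regulatory safety reporting, including the UADE assessment in Protocol 8.3.2. If the CEC already works in this way, the amendment simply records it.

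Nothing else needs to change for this point: treatment, follow-up, sample size, endpoint definitions and the analysis method all stay as they are. The cost is a small change to the wording of the protocol and the CEC charter, and to the order in which case material is released.

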11.0 ETHICAL and REGULATORY CONSIDERATIONS

11.1 Role of Medtronic

As the Sponsor of this clinical study, Medtronic has the overall responsibility for the conduct of the study, including assurance that the study will be conducted according to the International Conference on Harmonization (ICH) GCP guidelines, US FDA, Japan PMDA and local laws. In this study, Medtronic will have certain direct responsibilities and may delegate other responsibilities to consultants and/or contract research organizations.

The principles of the Declaration of Helsinki have all been implemented in this study by means of the subject informed consent process, IRB approval, study training, clinical trial registration, preclinical testing, risk benefit assessment, publication policy, etc.

11.2 General Duties

Medtronic's general duties consist of submitting applications and information to appropriate regulatory authorities, obtaining regulatory and IRB approvals prior to allowing shipment of devices, selecting qualified Investigators, ensuring proper clinical site monitoring, ensuring subject informed consent is obtained and ensuring that the IRB and relevant regulatory authorities are promptly notified of significant new information about the investigation.

Medtronic is responsible for providing quality data that satisfies regulations and informing Investigators, IRB and relevant regulatory authorities of UADEs/SADEs and deviations from the investigational plan as appropriate. The Medtronic Clinical Study Team will provide written progress reports and a final report.

11.3 Subject Confidentiality

Subject confidentiality will be maintained throughout the clinical study in a way that ensures the information can always be tracked back to the source data. For this purpose, a unique subject identification code (subject sequence number) will be assigned and used to allow identification of all data reported for each subject.

Study data may be made available to third parties, e.g., in the case of an audit performed by regulatory authorities, provided the data are treated confidentially and that the subject's privacy is guaranteed. The identity of a subject will never be disclosed in the event that study data are published.

The study sites in the US must comply with the subject confidentiality provisions of the Health Insurance Portability and Accountability Act (HIPAA) issued by the U.S. Department of Health and Human Services (HHS). Sites should maintain subject privacy in accordance to federal regulations (45 CFR Parts 160 and 164), local regulations, and institutional requirements.

11.4 Supplemental Applications

As appropriate, Medtronic will submit changes in the investigational plan to the appropriate regulatory authorities and to Investigators to obtain IRB re-approval as required.

RESOLUTE Onyx 2.0 mm Clinical Study**CONFIDENTIAL - May not be reproduced without written permission from Medtronic**

13.0 Appendices

RESOLUTE Onyx 2.0 mm Clinical Study
CONFIDENTIAL - May not be reproduced without written permission from Medtronic

Appendix 2: Acronyms, Abbreviations, and Definitions

Acronym/Abbreviation	Term
% DS	Percent diameter stenosis
ACC	American College of Cardiology
ACT	Activated clotting time
AE	Adverse event
AHA	American Heart Association
©	Copyright
CABG	Coronary artery bypass graft
CCSC	Canadian Cardiovascular Society Classification
CEC	Clinical Events Committee
CFR	Code of Federal Regulations
CK	Creatine kinase
CK-MB	Creatine kinase myocardial-band isoenzyme
CRF	Case report form
CRO	Contract Research Organization
DES	Drug eluting stent
DMC	Data Monitoring Committee
DS	Diameter stenosis
ECG	Electrocardiogram
EDC	Electronic data capture
FDA	Food and Drug Administration
FFR	Fractional Flow Reserve
GCP	Good Clinical Practices
GI	Gastrointestinal
HHS	US Department of Health and Human Services
HIPAA	Health Insurance Portability and Accountability Act
IRB	Institutional Review Board
ICH	International Conference on Harmonization
IFU	Instructions for Use
ITT	Intent-to-treat
IVUS	Intravascular ultrasound
LAD	Left anterior descending coronary artery
LCX	Left circumflex coronary artery
LIMA	Left internal mammary artery
LVEF	Left ventricular ejection fraction
MACE	Major adverse cardiac event
mg	Milligram
MI	Myocardial infarction
MLD	Minimum luminal/lumen diameter
µg	Microgram
Mm	Millimeter
MPI	Myocardial Perfusion Imaging
NTG	Nitroglycerin

RESOLUTE Onyx 2.0 mm Clinical Study**CONFIDENTIAL - May not be reproduced without written permission from Medtronic**

Acronym/Abbreviation	Term
PCI	Percutaneous coronary intervention
Plt	Platelet
PTCA	Percutaneous transluminal coronary angioplasty
QCA	Quantitative coronary angiography
QD	Every day
QWMI	Q wave myocardial infarction
RCA	Right coronary artery
RIMA	Right internal mammary artery
RVD	Reference vessel diameter
RX	Rapid exchange
SAE	Serious adverse event
SD	Standard deviation
TIA	Transient ischemic attack
TIMI	Thrombolysis in myocardial infarction
TLF	Target lesion failure
TLR	Target lesion revascularization
™	Trademark
TVF	Target vessel failure
TVR	Target vessel revascularization
UADE	Unanticipated adverse device effect
WBC	White blood cell
WHO	World Health Organization

RESOLUTE Onyx 2.0 mm Clinical Study
CONFIDENTIAL - May not be reproduced without written permission from Medtronic

Term	Definition
ACUTE CLOSURE	
Acute Closure:	Defined as the occurrence of new (during the procedure) severely reduced flow (TIMI grade 0-1) within the target vessel that persisted and required rescue by stenting or other treatment, or resulted in myocardial infarction or death. Abrupt closure requires proven association with a mechanical dissection of the treatment site or instrumented vessel, coronary thrombus, or severe spasm. Abrupt closure does not mean “no reflow” (due to microvascular flow limitation), in which the epicardial artery is patent but had reduced flow. Abrupt closure also does not mean transient closure with reduced flow in which the index treatment application does reverse the closure.
Subacute Closure:	Defined as abrupt closure that occurred after the procedure is completed (and the subject left the catheterization laboratory) and before the 30-day follow-up evaluation.
Threatened Acute Closure:	Defined as a grade B dissection and $\geq 50\%$ diameter stenosis or any dissection of grade C or higher.

ACUTE SUCCESS

All acute success data will be reported per Medtronic historical protocol definitions and current definitions listed below.

Device Success:

Medtronic historical definition: attainment of $< 50\%$ residual stenosis of the target lesion using only the study device.

Current definition: the attainment of $< 30\%$ residual stenosis by QCA (or $< 20\%$ by visual assessment) AND TIMI flow 3 after the procedure, using the study device only. These measurements will be made by the independent angiographic core laboratory. If the core laboratory is unable to assess the % residual stenosis, the investigator's assessment as recorded in the CRF will be used for the statistical analysis.

Lesion Success:

Medtronic historical definition: attainment of $< 50\%$ residual stenosis of the target lesion using any percutaneous method.

Current definition: the attainment of $< 30\%$ residual stenosis by QCA (or $< 20\%$ by visual assessment) AND TIMI flow 3 after the procedure, using any percutaneous method. These measurements will be made by the independent angiographic core laboratory. If the core laboratory is unable to assess the % residual stenosis, the investigator's assessment as recorded in the CRF will be used for the statistical analysis.

RESOLUTE Onyx 2.0 mm Clinical Study**CONFIDENTIAL - May not be reproduced without written permission from Medtronic**

Procedure Success:

Medtronic historical definition: attainment of < 50 % residual stenosis of the target lesion and no in-hospital MACE.

Current definition: the attainment of < 30% residual stenosis by QCA (or < 20% by visual assessment) AND TIMI flow 3 after the procedure, using any percutaneous method without the occurrence of MACE during the hospital stay. These measurements will be made by the independent angiographic core laboratory. If the core laboratory is unable to assess the % residual stenosis, the investigator's assessment as recorded in the CRF will be used for the statistical analysis.

Device Specific Procedure Success:

Device success and no in-hospital MACE.

ADVERSE EVENT

An adverse event is any untoward medical occurrence, unintended disease or injury, or untoward clinical signs (including abnormal laboratory findings) in subjects, users or other persons, whether or not related to the investigational medical device.

Note 1. This definition includes events related to the investigational medical device or the comparator.

Note 2. This definition includes events related to the procedures involved..

Note 3. For users or other persons, this definition is restricted to events related to investigational medical devices.

ANTICIPATED ADVERSE EVENT

Any undesirable experience (sign, symptom, illness, abnormal laboratory value, or other medical event) occurring to a subject, whether or not considered related to the investigational product(s) or drug regimen prescribed as part of the clinical protocol, predefined in the clinical protocol and/or IFU, that is identified or worsens during a clinical study.

BINARY ANGIOGRAPHIC RESTENOSIS

Defined as $\geq 50\%$ in-stent diameter stenosis at the follow-up angiogram. If an in-stent measurement is not available, the in-lesion diameter will be used.

CALCIFICATION

Calcification is defined as readily apparent radiopacities within the vascular wall at the site of the stenosis and is classified as none/mild, moderate (radiopacities noted only during the cardiac cycle before contrast injection), and severe (radiopacities noted without cardiac motion before contrast injection generally compromising both sides of the arterial lumen).

RESOLUTE Onyx 2.0 mm Clinical Study**CONFIDENTIAL - May not be reproduced without written permission from Medtronic****CANADIAN CARDIOVASCULAR SOCIETY CLASSIFICATION (CCSC) OF ANGINA^{49,10}**

- Class I** Ordinary physical activity does not cause angina, such as walking and climbing stairs. Angina with strenuous or rapid or prolonged exertion at work or recreation.
- Class II** Slight limitation of ordinary activity. Angina upon walking or climbing stairs rapidly, walking uphill, walking or stair climbing after meals, or in cold, or in wind, or under emotional stress, or only during the first hours after awakening. Angina if walking more than two blocks on the level and climbing more than one flight of ordinary stairs at a normal pace and in normal conditions.
- Class III** Marked limitations of ordinary physical activity. Walking one to two blocks on the level and climbing one flight of stairs in normal conditions and at a normal pace.
- Class IV** Inability to carry on any physical activity without discomfort. Angina syndrome may be present at rest.

CEREBROVASCULAR ACCIDENT (CVA) (see Stroke)**CLINICALLY-DRIVEN TARGET LESION REVASCULARIZATION (TLR)**

Revascularization at the target lesion associated with positive functional ischemia study or ischemic symptoms AND an angiographic minimal lumen diameter stenosis $\geq 50\%$ by QCA, or revascularization of a target lesion with diameter stenosis $\geq 70\%$ by QCA without either angina or a positive functional study.

CLINICALLY-DRIVEN TARGET VESSEL REVASCULARIZATION (TVR)

Revascularization in the target vessel associated with positive functional ischemia study or ischemic symptoms AND an angiographic minimal lumen diameter stenosis $\geq 50\%$ by QCA, or revascularization of a target vessel with diameter stenosis $\geq 70\%$ by QCA without either angina or a positive functional study.

***DE NOVO* LESION**

Defined as a lesion not previously treated.

RESOLUTE Onyx 2.0 mm Clinical Study**CONFIDENTIAL - May not be reproduced without written permission from Medtronic**

DEATH

All deaths are considered cardiac unless an unequivocal non-cardiac cause can be established. Specifically, any unexpected death even in subjects with coexisting potentially fatal non-cardiac disease (e.g. cancer, infection) should be classified as cardiac.

Cardiac death	Any death due to immediate cardiac cause (e.g. MI, low-output failure, fatal arrhythmia). Unwitnessed death and death of unknown cause will be classified as cardiac death. This includes all procedure related deaths including those related to concomitant treatment.
Vascular death	Death due to cerebrovascular disease, pulmonary embolism, ruptured aortic aneurysm, dissecting aneurysm, or other vascular cause.
Non-cardiovascular death	Any death not covered by the above definitions, including death due to infection, sepsis, pulmonary causes, accident, suicide or trauma.

DEVICE RELATED ADVERSE EVENT

A device related adverse event is defined as any adverse event for which a causal relationship between the event and the device implantation procedure, the presence of the device, or the performance of the device system, is at least a reasonable possibility (i.e., the relationship cannot be excluded).

DEVICE SUCCESS

Attainment of < 50 % residual stenosis of the target lesion using only the study device.

DEVICE SPECIFIC PROCEDURE SUCCESS

Device success and no in-hospital MACE.

DIABETES MELLITUS¹¹

Diabetes mellitus is a group of metabolic diseases characterized by hyperglycemia resulting from defects in insulin secretion, insulin action or both.

Three ways to diagnose diabetes are possible, and each must be confirmed, on a subsequent day, by any one of the three methods given:

1. Symptoms of diabetes plus casual plasma glucose concentration > 200 mg/dl (11.1 mmol/l). Casual is defined as any time of day without regard to time since last meal. The classic symptoms of diabetes include polyuria, polydipsia, and unexplained weight loss.
2. Fasting plasma glucose (FPG) > 126 mg/dl (7.0 mmol/l). Fasting is defined as no caloric intake for at least 8 hours.
3. Two hour post-load glucose (PG) > 200 mg/dl (11.1 mmol/l) during an oral glucose tolerance test (OGTT). The test should be performed as described by the World Health

RESOLUTE Onyx 2.0 mm Clinical Study**CONFIDENTIAL - May not be reproduced without written permission from Medtronic**

Organization (WHO)¹², using a glucose load containing the equivalent of 75 gm anhydrous glucose dissolved in water.

In the absence of unequivocal hyperglycemia with acute metabolic decompensation, these criteria should be confirmed by repeat testing on a different day. The third measure, OGTT, is not recommended for routine clinical use.

Medtronic working definition of diabetes mellitus: For the purposes of this trial a subject is considered to have a history of diabetes mellitus if he/she: is taking insulin, is taking oral antidiabetic agents, is on a modified diet to control diabetes mellitus, or has a diagnosis of diabetes mellitus documented in the medical record but is untreated, prior to the index procedure. Subjects who are taking insulin, or both insulin and oral agents, will be classified as insulin dependent. Subjects who are taking oral agents only, a modified diet only, both oral agents and a modified diet, or are currently untreated, will be classified as non-insulin dependent.

DISSECTION, NHLBI (National Heart, Lung, and Blood Institute) CLASSIFICATION¹³

- | | |
|----------------|---|
| Grade A | Small radiolucent area within the lumen of the vessel disappearing with the passage of the contrast material. |
| Grade B | Appearance of contrast medium parallel to the lumen of the vessel disappearing within a few cardiac cycles. |
| Grade C | Dissection protruding outside the lumen of the vessel persisting after passage of the contrast material. |
| Grade D | Spiral shaped filling defect with or without delayed run-off of the contrast material in the antegrade flow. |
| Grade E | Persistent luminal filling defect with delayed run-off of the contrast material in the distal lumen. |
| Grade F | Filling defect accompanied by total coronary occlusion. |

EMERGENT BYPASS SURGERY

Defined as coronary bypass surgery performed on an urgent or emergent basis for severe vessel dissection or closure, or treatment failure resulting in new ischemia.

FRACTIONAL FLOW RESERVE

A measurement of blood flow and blood pressure to determine the need for PCI.

INCOMPLETE APPPOSITION

Failure of the stent to completely appose to the vessel wall after placement. Defined as one or more stent struts separated from the vessel wall with evidence of blood speckles behind the strut in the ultrasound image.

RESOLUTE Onyx 2.0 mm Clinical Study
CONFIDENTIAL - May not be reproduced without written permission from Medtronic

LATE LUMEN/LUMINAL LOSS

Defined as the difference between the post-procedure minimal lumen diameter (MLD) and the follow-up angiography MLD.

LESION CLASS (American College of Cardiology/American Heart Association Class)¹⁴

- Type A Lesions:** Minimally complex, discrete (length < 10 mm), concentric, readily accessible, non-angulated segment (< 45°), smooth contour, little or no calcification, less than totally occlusive, not ostial in location, no major side branch involvement, and an absence of thrombus.
- Type B Lesions:** Moderately complex, tubular (length 10 to 20 mm), eccentric, moderate tortuosity of proximal segment, moderately angulated segment (> 45°, < 90°), irregular contour, moderate or heavy calcification, total occlusions < 3 months old, ostial in location, bifurcation lesions requiring double guidewires, and some thrombus present.
- Type B1:* One adverse characteristic.
- Type B2:* Two or more adverse characteristics.
- Type C Lesions:** Severely complex, diffuse (length > 20 mm), excessive tortuosity of proximal segment, extremely angulated segments > 90°, total occlusions > 3 months old and/or bridging collaterals, inability to protect major side branches, and degenerated vein grafts with friable lesions.

LESION SUCCESS

Attainment of < 50 % residual stenosis of the target lesion using any percutaneous method.

MAJOR ADVERSE CARDIAC EVENTS (MACE)

Defined as death, myocardial infarction (Q wave and non-Q wave), emergent coronary bypass surgery, or clinically-driven repeat target lesion revascularization by percutaneous or surgical methods.

MINIMAL LUMINAL DIAMETER (MLD)

The average of two orthogonal views (when possible) of the narrowest point within the area of assessment – in lesion, in stent or in segment. MLD is visually estimated during angiography by the Investigator; it is measured during QCA by the Angiographic Core Laboratory.

MYOCARDIAL INFARCTION (MI)

All myocardial infarction data will be reported per Medtronic historical protocol definitions.

RESOLUTE Onyx 2.0 mm Clinical Study
CONFIDENTIAL - May not be reproduced without written permission from Medtronic

Q wave MI (QWMI): will require one of the following criteria:

Chest pain or other acute symptoms consistent with myocardial ischemia and new pathological Q waves in two or more contiguous ECG leads as determined by an ECG core laboratory or independent review of the CEC, in the absence of timely cardiac enzyme data.

New pathologic Q waves in two or more contiguous ECG leads as determined by an ECG core laboratory or independent review of the CEC and elevation of cardiac enzymes. In the absence of ECG data the CEC may adjudicate Q wave MI based on the clinical scenario and appropriate cardiac enzyme data.

Medtronic Historical Definition of Non-Q Wave MI (NQWMI): elevated CK $\geq 2X$ the laboratory upper limit of normal with the presence of an elevated CK-MB (any amount above the laboratory upper limit of normal) in the absence of new pathological Q waves.

Extended Historical Definitions:

I. PCI (PERCUTANEOUS CORONARY INTERVENTION)

Ia. Baseline Biomarkers of Myocardial Damage (CK and CKMB and Trop $< 1*URL$) and not acute MI in progress.

PERIPROCEDURAL <48 HOURS POST PCI

A. New pathologic q waves in ≥ 2 contiguous ECG leads AND:
 
 ▪ any CKMB $> 1*URL$ or ▪ in the absence of CKMB: Troponin $> 1*URL$ or ▪ in the absence of CKMB and Troponin: CK $> 1*URL$ or ▪ in the absence of CKMB and Troponin and CK: CEC decision upon clinical scenario 
B. Appropriate cardiac enzyme data (respecting top-down hierarchy, b1 to b3):
 
b1. CK $\geq 2* URL$ Confirmed by :
 
 ▪ CKMB $> 1*URL$ or ▪ in the absence of CKMB:, Troponin $> 1*URL$ or ▪ in the absence of CKMB and Troponin: CEC decision upon clinical scenario 
OR
 
b2. In the absence of CK: CKMB $> 3*URL$
 
OR
 
b3. In the absence of CK and CKMB: Troponin $> 3*URL$

Note: URL = upper reference limit, defined as 99th percentile of normal reference range

RESOLUTE Onyx 2.0 mm Clinical Study**CONFIDENTIAL - May not be reproduced without written permission from Medtronic****Ib. If Baseline Biomarkers of Myocardial Damage: CK and/or CKMB > 1*URL *or* acute MI in progress****MYOCARDIAL INFARCTION, RE-INFARCTION (EXTENSION) <48 HOURS POST PCI**

A. If CK (or CKMB) from index MI has not yet reached its maximum level:

- Recurrent thoracic chest pain or ischemia equivalent >20 minutes (or new ECG changes consistent with MI)

AND

▪ Appropriate cardiac enzyme data:

- A rise in CK within 24 hours of the index event >2*URL (confirmed by either CKMB or Troponin > 1*URL) and ≥ 50% above the previous level *or*
- In absence of CK: a (post PCI) rise in CKMB within 24 hours of the index event >3*URL and ≥ 50% above the previous level *or*
- In absence of CK and CKMB: a (post PCI) rise of Troponin within 24 hours of the index event >3*URL and ≥ 50% above the previous level.

B. If elevated CK (or CKMB) following the index MI has peaked **AND** CK level has returned < URL then any new rise in:

- CK >2*URL (confirmed by either CKMB > URL or Troponin >URL) *or*
- in the absence of CK: CKMB > 3*URL *or*
- in the absence of CK and CKMB, Troponin > 3*URL

C. If CK (or CKMB) following the index MI has peaked **AND** CK level has NOT returned to < URL:

- A rise in CK ≥50% above the previous level and > 2 URL confirmed by either CKMB > URL or Troponin > URL. *or*
- In absence of CK, when CKMB has NOT returned < URL, a rise in CKMB ≥50% above the previous level and > 3 URL. *or*
- In absence of CK, when CKMB and Troponin has not returned < URL a rise in Troponin ≥ 50% above the previous level and >3*URL

RESOLUTE Onyx 2.0 mm Clinical Study**CONFIDENTIAL - May not be reproduced without written permission from Medtronic****SPONTANEOUS MI >48 HOURS (PCI)**

- A. Recurrent thoracic chest pain or ischemic equivalent **AND**
- New pathologic q waves in ≥ 2 contiguous ECG leads **AND** any CKMB $> 1*$ URL. **or**
 - in the absence of CKMB: Troponin $> 1*$ URL **or**
 - in the absence of CKMB and Troponin: CK $> 1*$ URL **or**
 - in the absence of CKMB and Troponin and CK: CEC decision upon clinical scenario
- B. Appropriate cardiac enzyme data (respecting top-down hierarchy):
- b1. CK $\geq 2*$ URL Confirmed by:
- CKMB $> 1*$ URL **or**
 - in the absence of CKMB: Troponin $> 1*$ URL **or**
 - in the absence of CKMB and Troponin: CEC decision upon clinical scenario
- OR**
- b2. In the absence of CK: CKMB $> 3*$ URL
- OR**
- b3. In the absence of CK and CKMB: Troponin $> 3*$ URL
- OR**
- b4. In the absence of CK, CK-MB and Troponin, clinical decision based upon clinical scenario.

II. CABG (CORONARY ARTERY BYPASS GRAFTING)**IIa. Baseline Biomarkers of Myocardial Damage (CK and CKMB and Trop $< 1*$ URL) and not acute MI in progress.****PERIPROCEDURAL <72 HOURS POST CABG**

- A. New pathologic q waves in ≥ 2 contiguous ECG leads or recurrent signs or symptoms consistent with myocardial ischemia **AND**
- CK-MB $> 5x$ URL **or**
 - in the absence of CKMB: Troponin $> 5*$ URL **or**
 - in the absence of CKMB and Troponin: CK > 5 URL **or**
 - in the absence of CKMB and Troponin and CK: CEC decision upon clinical scenario
- B. Appropriate cardiac enzyme data
- CKMB $\geq 10*$ URL **or**
 - In the absence of CKMB: Trop $> 10*$ URL. **or**
 - In the absence of CKMB and Troponin: CK $> 10*$ URL

RESOLUTE Onyx 2.0 mm Clinical Study
CONFIDENTIAL - May not be reproduced without written permission from Medtronic

IIIb. If Baseline Biomarkers of Myocardial Damage: CK and/or CKMB > 1*URL *or* acute MI in progress

MYOCARDIAL INFARCTION, RE-INFARCTION (EXTENSION) <72 HOURS POST CABG

- A. If Peak CK (or CKMB) from index MI has not yet reached its maximum level:
- Clinical signs or symptoms consistent with recurrent myocardial ischemia
AND
 - Appropriate cardiac enzyme data:
 - A rise in CKMB within 24 hours of the index event >10*URL and ≥ 50% above the previous level.
 - In absence of CKMB: a rise in Troponin within 24 hours of the index event >10*URL and ≥ 50% above the previous level.
 - In absence of CKMB and Troponin: a rise in CK within 24 hours of the index event >10*URL and ≥ 50% above the previous level.
- B. If elevated CK (or CKMB) following the index MI has peaked *AND* CKMB level has returned < URL, any new rise in:
- CKMB >10*URL *or*
 - in the absence of CKMB: Troponin > 10*URL *or*
 - in the absence of CKMB and Troponin: CK > 10*URL
- C. If elevated CK (or CKMB) following the index MI has peaked *AND* CKMB level has NOT returned < URL:
- A rise in CKMB ≥50% above the previous level and > 10 URL *or*
In absence of CKMB: a rise in Troponin ≥50% above the previous level and > 10*URL. *or*
 - In absence of CKMB and Troponin: a rise in CK ≥ 50% above the previous level and >10*URL

MYOCARDIAL PERFUSION IMAGING

A type of nuclear stress test used to identify areas of the heart that aren't getting enough blood using radioactive tracers and electrodes.

NO REFLOW

Defined as a sustained or transient reduction in antegrade flow that is not associated with an obstructive lesion at the treatment site.

PERCENT DIAMETER STENOSIS

The value calculated as $100 \times (RVD - MLD)/RVD$ using the mean values from two orthogonal views (when possible) by QCA.

RESOLUTE Onyx 2.0 mm Clinical Study
CONFIDENTIAL - May not be reproduced without written permission from Medtronic

PERFORATION

Perforations will be classified as follows:

- Angiographic perforation:** perforation detected by the clinical site or the core laboratory at any point during the procedure.
- Clinical perforation:** perforation requiring additional treatment (including efforts to seal the perforation or pericardial drainage), or resulting in significant pericardial effusion, acute closure, myocardial infarction, or death.
- Pericardial hemorrhage/tamponade:** perforation resulting in cardiac tamponade.

PROCEDURE SUCCESS

Attainment of < 50 % residual stenosis of the target lesion and no in-hospital MACE.

RESTENOTIC LESION

Defined as a lesion in a vessel segment that has undergone prior percutaneous treatment with or without a stent placement.

REFERENCE VESSEL DIAMETER (RVD)

Defined as the average of normal segments within 10 mm proximal and distal to the target lesion from two orthogonal views using QCA.

SERIOUS ADVERSE EVENT

A serious adverse event (SAE) is defined as an adverse medical occurrence that:

- a) led to death
- OR
- b) led to a serious deterioration in the health of a subject that either resulted in
 - 1) a life-threatening illness or injury, or
 - 2) a permanent impairment of a body structure or a body function, or
 - 3) in-patient or prolonged hospitalization, or
 - 4) medical or surgical intervention to prevent life-threatening illness or injury or permanent impairment to body structure or a body function
- OR
- c) led to fetal distress, fetal death or a congenital abnormality or birth defect.

RESOLUTE Onyx 2.0 mm Clinical Study**CONFIDENTIAL - May not be reproduced without written permission from Medtronic**

STENT THROMBOSIS

All stent thrombosis data will be reported per the Academic Research Consortium (ARC) definitions.

Academic Research Consortium (ARC) Definition:

Stent thrombosis should be reported as a cumulative value over time and at the various individual time points as specified below. Time 0 is defined as the time point after the guiding catheter has been removed and the subject has left the catheterization lab.

Timing:

Acute stent thrombosis *	0 – 24 hours post stent implantation
Subacute stent thrombosis *	> 24 hours – 30 days post stent implantation
Late stent thrombosis	> 30 days – 1 year post stent implantation
Very late stent thrombosis	> 1 year post stent implantation

* Acute or subacute stent thrombosis can also be replaced by the term early stent thrombosis.

Three categories of evidence define stent thrombosis: *Definite, Probable, Possible*

